2.2 Analysis sets

Full Analysis Set

The FAS comprises all patients to whom study treatment has been assigned by randomization regardless of whether or not treatment was administered. According to the intent to treat principle, patients will be analyzed according to the treatment they have been assigned to during the randomization procedure. This population will be the primary population for efficacy analyses.

Safety Set

The **Safety Set** includes all patients who received at least one dose of any component of the study treatment. Subjects will be analyzed according to the study treatment they actually received where treatment received is defined as the randomized treatment if the patient took at least one dose of that treatment or the first treatment received if the randomized treatment was never received.

Evaluable Set

The **Evaluable Set** (ES) consists of all evaluable patients in the FAS who meet all of the following four criteria:

- centrally confirmed measurable disease, and
- centrally confirmed positive BRAF V600 mutation, and
- an adequate tumor assessment at baseline (An adequate tumor assessment at baseline refers to baseline measurable disease assessed by investigator and confirmed by central independent reviewer per RANO criteria), and
- either 1) a follow-up tumor assessment at week 8 day 1 visit or later (any assessment on or after day 43 allowing for the time-window around the visit) or 2) disease progression at any time or 3) have discontinued for any reason.

The evaluable set will be used for sensitivity analyses as defined in Section 2.5 and Section 2.7.

Crossover Set

The **Crossover Set** (CS) comprises the subset of patients who were randomized to carboplatin with vincristine control arm and elected to crossover to receive dabrafenib in combination with trametinib treatment after centrally confirmed and RANO-defined disease progression. Only subjects who received at least one dose of crossover treatment will be included in the crossover set.

Patient Classification:

Patients may be excluded from the analysis populations defined above based on specific patient classification rules defined in Table 2-6. Reasons leading to exclusion from analysis sets will be listed.

	-
Analysis set	Criteria leading to exclusion
FAS	Not applicable
Safety Set	No dose of study medication
Evaluable Set	Not centrally confirmed measurable disease at baseline,
	Not centrally confirmed BRAF V600 mutant,
	Patients who do not have an adequate tumor assessment at baseline
	Patients who do not have a follow-up tumor assessment at least 43 days after starting treatment unless disease progression is observed before that time or patient discontinued for any reason.

Table 2-6 Patient classification rules for analysis sets

Withdrawal of Informed Consent

Any data collected in the clinical database after a patient withdraws informed consent from all further participation in the trial, will not be included in the analysis data sets. The date on which a patient withdraws full consent is recorded in the eCRF.

Death events may be used in the analysis if captured from public records (registers), local law and subject informed consent permitting.

Additional data for which there is a separate informed consent, collected in the clinical database without having obtained that consent will not be included in the analysis. These data will be excluded by the presence of the appropriate protocol deviation criterion.

2.2.1 Subgroups of interest

Efficacy

No subgroup analyses of efficacy data are planned for the final CSR.

Safety

Safety subgroup analyses will use the same method as for the analysis in the safety analysis set. Key safety analyses including:

- Overview of AEs:
 - AEs, regardless of relationship to study drug, by primary system organ class (SOC) and preferred term (PT)
 - AEs related to the study drug, by primary SOC and PT

Novartis	Confidential	Page 19
SAP Final CSR LGG		CDRB436G2201

• Serious AEs, regardless of relationship to study drug, by primary SOC and PT

will be repeated on safety set in the following subgroups:

• Age group at enrollment (12 months- <6 years, 6 -< 12 years, 12 -< 18 years)

The objective for carrying out these subgroup analyses is to identify potential safety issues that may be limited to a subgroup of patients, or safety issues that are more commonly observed in a subgroup of patients.

2.3 Patient disposition, demographics and other baseline characteristics

The FAS will be used for all baseline and demographic summaries and listings unless otherwise specified. Summaries will be reported by treatment group and for all patients, and listings will be reported by treatment group to assess baseline comparability. No inferential statistics will be provided.

For this final analysis, no analyses will be performed on basic demographic and background data, diagnosis and extent of cancer, medical history or other baseline data. As there have been no changes to patient enrollment since the primary analysis, the analyses performed for the primary analysis can be referred to for all baseline data.

2.3.1 Patient disposition

The number (%) of patients in the FAS who completed treatment, who discontinued the study phases and the reason for discontinuation will be presented overall and by treatment group.

The following summaries will be provided: % based on the total number of FAS patients:

- Number (%) of patients who were randomized (based on data from IRT system);
- Number (%) of patients who were randomized but not treated (based on 'DAR' eCRF page not completed for any study treatment component);
- Primary reason for not being treated (based on 'End of Treatment Disposition' eCRF page);
- Number (%) of patients who were treated (based on 'DAR' eCRF pages of each study treatment component completed with non-zero dose administered);
- Number (%) of patients who completed treatment (based on the 'End of Treatment Disposition' page not completed);
- Number (%) of patients who completed treatment and do not have RANO-defined progression of disease assessed by investigator (based on the 'End of Treatment Disposition' page not completed and no PD reported on the RANO pages);
- Number (%) of patients who are completed treatment post RANO-defined progression of disease assessed by investigator (based on the 'Confirmation of Favorable Clinical Benefit from Study Treatment' page, the 'End of Treatment Disposition' not completed , and PD reported on the RANO pages);
- Number (%) of patients who discontinued the study treatment phase (based on the 'End of Treatment Disposition' page)

- Primary reason for study treatment phase discontinuation (based on the 'End of Treatment Disposition' page)
- Number (%) of patients who have entered the post-treatment follow-up (based on the 'End of Treatment Disposition' page);
- Number (%) of patients who have discontinued from the post-treatment follow-up (based on the 'End of Post Treatment Phase Disposition' page);
- Reasons for discontinuation from the post-treatment follow-up (based on 'End of Post Treatment Phase Disposition' page);
- Number (%) of patients who have entered the survival follow-up (based on the 'End of Treatment Phase' or 'End of Post Treatment Phase Disposition' page).
- Number (%) of patients who have enrolled in the long-term follow-up study G2401. (based on the 'EOT_Rollover' disposition page).

Protocol deviations

The number (%) of patients in the FAS with any protocol deviation will be tabulated by deviation category (as specified in the study Data Handling Plan) overall and by treatment group. All protocol deviations will be listed.

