2.3.1 Patient disposition

The number (%) of patients in the FAS who completed treatment, who discontinued the study phases and the reason for discontinuation will be presented.

The following summaries will be provided: % based on the total number of FAS patients:

- Number (%) of patients who were treated (based on 'DAR' eCRF pages of each study treatment component completed with non-zero dose administered);
- Number (%) of patients who completed the study treatment phase (based on the 'End of Treatment Disposition' page)
- Number (%) of patients who discontinued the study treatment phase (based on the 'End of Treatment Disposition' page)
- Primary reason for study treatment phase discontinuation (based on the 'End of Treatment Disposition' page)
- Number (%) of patients who have entered the post-treatment follow-up (based on the 'End of Treatment Disposition' page);

- Number (%) of patients who have discontinued from the post-treatment follow-up (based on the 'End of Post Treatment Phase Disposition' page);
- Reasons for discontinuation from the post-treatment follow-up (based on 'End of Post Treatment Phase Disposition' page);
- Number (%) of patients who have entered the survival follow-up (based on the 'End of Treatment Disposition' or 'End of Post Treatment Phase Disposition' page).
- Number (%) of patients who have rolled over to long-term follow-up study G2401. (based on the 'EOT_Rollover' disposition page).

Protocol deviations

The number (%) of patients in the FAS with any protocol deviation will be tabulated by deviation category (as specified in the study Data Handling Plan). All protocol deviations will be listed.

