5.1 Imputation rules

5.1.1 Study drug

The following rule should be used for the imputation of date of last administration for a given study treatment component:

Scenario 1: If the date of last administration is completely missing and there is no EOT eCRF page and no death date, the patient is considered as on-going:

The patient should be treated as on-going and the cut-off date should be used as the last dosing date.

Scenario 2: If the date of last administration is completely or partially missing and the EOT eCRF page is available (prior to any death date or withdrawal of consent date, if available):

Case 1: The date of last administration is completely missing, and the EOT visit date is complete, then this latter date should be used.

Case 2: Only Year (yyyy) of the dose end date is available and yyyy < the year of EOT date:

Use Dec31yyyy

Case 3: Only Year(yyyy) of the dose end date is available and yyyy = the year of EOT date:

Use EoT date

Case 4: Both Year(yyyy) and Month (mm) are available for the date of last administration, and yyyy = the year of EOT date and mm < the month of EOT date:

Use last day of the Month (mm)

All other cases should be considered as a data issue and the statistician should contact the data manager of the study.

After imputation, compare the imputed date with start date of that specific record, if the imputed date is < start date of that record:

Use the start date of that record

Patients with missing start dates are to be considered missing for all study treatment component related calculations and no imputation will be made. If the date of first administration is missing, then the date of last administration should not be imputed.

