2.3.1 Patient disposition

Enrollment by country and center will be summarized for all screened patients and also by treatment group using the FAS. The number (%) of randomized patients included in the FAS will be presented overall and by treatment group. The number (%) of screened and notrandomized patients and the reasons for screening failure will also be displayed. The number (%) of patients in the FAS who are still on treatment, who discontinued the study phases and the reason for discontinuation will be presented overall and by treatment group.

The following summaries will be provided: % based on the total number of FAS patients:

- Number (%) of patients who were randomized (based on data from IRT system);
- Number (%) of patients who were randomized but not treated (based on 'DAR' eCRF page not completed for any study treatment component);
- Primary reason for not being treated (based on 'End of Treatment Disposition' eCRF page);
- Number (%) of patients who were treated (based on 'DAR' eCRF pages of each study treatment component completed with non-zero dose administered);
- Number (%) of patients who are still on-treatment (based on the 'End of Treatment Disposition' page not completed);
- Number (%) of patients who are still on-treatment and do not have RANO-defined progression of disease assessed by investigator (based on the 'End of Treatment Disposition' page not completed and no PD reported on the RANO pages);
- Number (%) of patients who are still on-treatment post RANO-defined progression of disease assessed by investigator (based on the 'Confirmation of Favorable Clinical Benefit from Study Treatment' page, the 'End of Treatment Disposition' not completed , and PD reported on the RANO pages);
- Number (%) of patients who discontinued the study treatment phase (based on the 'End of Treatment Disposition' page)
- Primary reason for study treatment phase discontinuation (based on the 'End of Treatment Disposition' page)
- Number (%) of patients who have entered the post-treatment follow-up (based on the 'End of Treatment Disposition' page);
- Number (%) of patients who have discontinued from the post-treatment follow-up (based on the 'End of Post Treatment Phase Disposition' page);
- Reasons for discontinuation from the post-treatment follow-up (based on 'End of Post Treatment Phase Disposition' page);

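### The LGG final SAP relabels 'still on-treatment' as 'completed treatment' but keeps the old derivation, so the disposition table leaves out chemotherapy completers

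*SAP*

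**What the plan says.** The opening sentence of Section 2.3.1 in the LGG final SAP promises the number of FAS patients who completed treatment, overall and by treatment group. Three consecutive rows follow:

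- the overall row, "Number (%) of patients who completed treatment (based on the 'End of Treatment Disposition' page not completed", which carries no further condition;
- a first split, "Number (%) of patients who completed treatment and do not have RANO-defined progression of disease assessed by investigator", again conditional on the page not being completed, with no PD on the RANO pages;
- a second split, "Number (%) of patients who are completed treatment post RANO-defined progression of disease assessed by investigator", again conditional on the page not being completed, with PD reported and the page confirming favorable clinical benefit.

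The same section reads two other rows from this page: "Number (%) of patients who discontinued the study treatment phase (based on the 'End of Treatment Disposition' page" and "Number (%) of patients who have entered the post-treatment follow-up (based on the 'End of Treatment Disposition' page". A separate row counts patients who enrolled in the long-term follow-up study G2401, from the EOT_Rollover page.

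**The concern.** An End of Treatment page that has not been filled in normally means that the patient is still on drug or that the form is missing. It does not show that planned treatment was finished. Carboplatin with vincristine has a planned end: Section 1.1 gives a 12-week induction course and 8 maintenance cycles of 6 weeks, so 12 + 8 × 6 = 60 weeks. Completion is therefore a real outcome in the control arm, and a reader will look to the disposition table for it. A rule that selects on the absence of the page cannot supply that number, and it may move the completers into the discontinuation row.

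**Working it through.** No sample size, power or event figure is involved, so the check sets the passages side by side.

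**1. Where the condition came from.** LGG SAP Amendment 1, Section 2.3.1, has "Number (%) of patients who are still on-treatment (based on the 'End of Treatment Disposition' page not completed", followed by the same two splits by investigator-assessed progression. At a primary analysis with patients still on drug, an unfilled page is a sensible marker of ongoing treatment. The final SAP changed the label in all three rows and kept the condition in all three. The grammar of "Number (%) of patients who are completed treatment post RANO-defined progression of disease assessed by investigator" looks like a trace of that substitution.

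**2. How the final SAP reads an absent page elsewhere.** In Section 5.1.1, Scenario 1, the date of last administration is completely missing and there is neither an End of Treatment page nor a death date. The instruction is: "The patient should be treated as on-going and the cut-off date should be used as the last dosing date". There an absent page goes with ongoing treatment; in Section 2.3.1 it means completed treatment.

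**3. How the other cohort handles it.** The HGG final SAP, Section 2.3.1, has "Number (%) of patients who completed the study treatment phase (based on the 'End of Treatment Disposition' page", with no 'not completed' condition. It too has a separate EOT_Rollover row.

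**4. What happens to a chemotherapy completer.**
- Section 1.1 of the LGG final SAP: patients who complete carboplatin with vincristine without RANO progression continue tumor assessments in post-treatment follow-up.
- Section 2.3.1: entry to post-treatment follow-up is read from the End of Treatment Disposition page.
- Such a patient therefore has the page filled in and fails the condition in the first two 'completed' rows. The third requires PD, so it does not apply.
- The discontinuation row reads the same page and states no status or reason filter, so the patient may be counted there instead.

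**5. Who does meet the condition.** Section 2.1 sets the final cut-off at last patient last visit. Patients without the page at that point are those with a missing form and, if rollover patients have only the EOT_Rollover page, the rollovers. If every treated patient has the page, treated patients contribute 0 to the row in each arm.

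**6. Scale.** Planned enrollment is about 102 at 2:1, so 102 × 2/3 = 68 on dabrafenib plus trametinib and 102 × 1/3 = 34 on chemotherapy. The number of control patients wrongly left out equals the number of true completers who have the page, anywhere from 0 to about 34. The SAP does not give the actual number.

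**The case against.** The case for leaving this alone is that it is a leftover edit in one descriptive table, conspicuous at output review, with the substance reported elsewhere. Much of that stands. Section 2.4.1 derives the number of maintenance cycles from dose counts, summarizes exposure and relative dose intensity separately for induction and maintenance, and reports permanent discontinuations with reasons from the dosing pages. Comparator delivery can be judged without this row. The third row also relies on a page about continuing treatment beyond progression, which Section 1.1 describes for dabrafenib plus trametinib patients, so not all three rows are about chemotherapy.

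Four stronger readings are tempting and are not supported:

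- *The flag is simply inverted.* Patients with the page include early discontinuers as well as completers, so negating the condition would not give the completers either. This is a stale derivation under a new label.
- *The row will show 0%.* That holds only if every treated patient has the page. The SAP does not say whether rollover patients have it as well as the EOT_Rollover page; if they do not, the row would count rollovers.
- *ORR or PFS is affected.* No response, PFS, DOR, TTR or censoring definition in Sections 2.5 and 2.7 uses this flag, and the final analysis is descriptive.
- *The HGG final SAP states a completion-status rule.* It says only that completion is based on the page.

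What does not stand is that review will put it right. Three rows state the condition explicitly, and a program written to specification would follow it. The rollover explanation does not rescue the rule either: it would count patients who moved to the follow-up study as completers while still leaving out those who finished planned chemotherapy without progression.

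**Conclusion.** The point holds for the disposition table. The final SAP kept a condition that identified ongoing patients and now calls the result completed treatment, in three rows and both arms. Applied as written, it excludes chemotherapy completers without progression, and they may appear as discontinued. The row would be about 0% in both arms if all treated patients have the page; otherwise it counts missing forms or rollovers.

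This rests on reading the rows literally and on the follow-up entry row meaning that the page is filled for those patients. The eCRF fields are not shown, so a recorded completion status is inferred, with support from the HGG final SAP. The size is bounded only by the planned control arm of about 34. It should be corrected before the table is produced; it does not alter any efficacy result.

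**What to change.** In LGG final SAP Section 2.3.1:

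1. Derive 'completed treatment' from the End of Treatment Disposition page being present with a status or reason of completion. Confirm the field name against the eCRF.
2. Split completers by investigator RANO PD present or absent on the response pages, replacing the derivation in the second and third rows.
3. Restrict the discontinuation row and its primary-reason row to non-completion reasons, so that no patient is counted as both completed and discontinued.
4. Keep the 'page not completed' condition only for a row labelled ongoing, rolled over or form missing, if one is wanted.

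The cost is rewording a few bullets and reprogramming the completion flag, with a matching filter on the discontinuation rows. No new data are needed if the page records completion.

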2.4 Treatments (study treatment, rescue medication, concomitant therapies, compliance)

2.4.1 Study treatment / compliance

Duration of exposure, actual cumulative dose, dose intensity (DI) and relative dose intensity (RDI) will be summarized by treatment group, separately for each component of study treatment (dabrafenib, trametinib, carboplatin, and vincristine). The duration of exposure will also be presented for the study treatment. Duration of exposure will be categorized into time intervals; frequency counts and percentages will be presented for the number (%) of patients in each interval. The number (%) of patients who have dose reductions or interruptions, and the reasons, will be summarized by treatment group. The number (%) of patients with a dose re-escalation will also be summarized by treatment group.

Patient level listings of all doses administered on treatment along with dose change reasons will be produced.

The safety set will be used for all summaries and listings of study treatment.

Duration of exposure to study treatment

Duration of exposure to study treatment is considered by taking into account the duration of exposure to any combination partner.

Duration of exposure to study treatment (days) = (last date of exposure to study treatment) - (date of first administration of study treatment) + 1.

The last date of exposure to study treatment is the latest of the last dates of exposure to any combination partner (see Table 2-7 Definition of last date of exposure of study drug).

Novartis	Confidential	Page 21
SAP Final CSR LGG		CDRB436G2201

Summary of duration of exposure of study treatment in appropriate time units based on clinically meaningful time intervals (eg 8-<24, 24-<56, 56-<112, \geq 112 (weeks)) will include categorical summaries and continuous summaries (i.e. n, mean, standard deviation, median, 25th-75th percentiles, minimum, and maximum) using appropriate units of time.

Duration of exposure to combination partner

Duration of exposure to dabrafenib (days) = (last date of exposure to dabrafenib) – (date of first administration of dabrafenib) + 1.

Duration of exposure to trametinib (days) = (last date of exposure to trametinib) – (date of first administration of trametinib) + 1.

Duration of exposure to carboplatin overall (days) = (last date of exposure to carboplatin as defined in Table 2-7) – (date of first administration of carboplatin) + 1.

Duration of exposure to vincristine overall (days) = (last date of exposure to vincristine as defined in Table 2-7) – (date of first administration of vincristine) + 1.

Induction phase:

Carboplatin is dosed as weekly IV infusions on weeks 1 to 4, and on weeks 7 to 10 followed by 2 weeks of rest in the *induction phase*. Vincristine is dosed as weekly IV bolus infusion for 10 weeks followed by 2 weeks of rest in the *induction phase*. The induction phase refers to the first 12 weeks of dosing (i.e from day of first dose of carboplatin or vincristine until 84 days).

The *last date of exposur* to carboplatin or vincristine in the induction phase is calculated including the rest periods (2 weeks). If subjects continued on to maintenance therapy, the last date of exposure in induction phase is the day before the start of maintenance therapy. If the subject does not continue on to maintenance therapy, the last date of exposure is calculated using the planned cycle duration, i.e. the last date of exposure is the date of first administration (of carboplatin or vincristine) in induction + 83 days. If the subject dies or if the data cutoff date is prior to the calculated date of last exposure, the date will be capped at the date of death or data cutoff.

Maintenance phase:

Maintenance phase will continue for up to a total of 8 cycles, each cycle will be 6 weeks in duration and consists of 4 weekly doses of carboplatin followed by 2 weeks of rest, and three weekly doses of vincristine given concomitantly with the first 3 weeks of carboplatin , followed by three weeks of rest. The maintenance phase refers to the dosing after the first 12 weeks, and will be identified by having at least 9 non-zero doses of Carboplatin, or at least 11 non-zero doses of Vincristine. For Carboplatin/Vincristine, maintenance cycle week1 dates are defined by the following non-zero doses: dose 9/dose 11, dose 13/dose 14, dose 17/dose 17, dose 21/dose 20, dose 25/dose 23, dose 29/dose 26, dose 33/dose 29, and dose 37/dose 32, respectively.

The *last date of exposur* to carboplatin or vincristine in the induction phase is calculated including the rest periods (2 or 3 weeks). The last date of exposure is calculated using the planned cycle duration, i.e. the last date of exposure is the date of last week 1 administration (of carboplatin or vincristine) in maintenance +41 days. If the subject dies or if the data cutoff

date is prior to the calculated date of last exposure, the date will be capped at the date of death or data cutoff. The *number of cycles* of maintenance therapy will be determined as the following total number of non-zero doses:

- Carboplatin: 1 cycle 9 to 12 doses; 2 cycles 13-16 doses; 3 cycles 17 to 20 doses; 4 cycles 21 to 24 doses; 5 cycles 25 to 28 doses; 6 cycles 29 to 32 doses; 7 cycles 33 to 36 cycles; 8 cycles ≥ 37 doses.
- Vincristine: 1 cycle 11 to 13 doses; 2 cycles 14-16 doses; 3 cycles 17 to 19 doses; 4 cycles 20 to 22 doses; 5 cycles 23 to 25 doses; 6 cycles 26 to 28 doses; 7 cycles 29 to 31 cycles; 8 cycles ≥ 32 doses.

Duration of exposure to carboplatin and vincristine (days) will be calculated by treatment phase (induction and maintenance phase) and overall (if applicable) as:

Duration of [study drug] exposure (days) in induction phase = (Date of first week1 dose of [study drug] in maintenance -1 day) - (date of first administration of [study drug]) + 1, for those who entered maintenance. For those who did not enter maintenance therapy, duration of maintenance will be defined as [minimum (date of first administration of [study drug] + 83 days, date of death, date of data cutoff) - (date of first administration of [study drug]) + 1.

Duration of [study drug] exposure (days) in maintenance phase = [minimum(Date of last week1 dose of [study drug] in maintenance + 41 days, date of death, date of data cutoff)] - (date of first week1 dose of [study drug] in maintenance) + 1.

	Deminion of last date of expectate of study and				
Scenario	Definition of last date of exposure of study drug	Example			
Carboplatin, Vincristine	The planned end date of the last cycle in which the last non-zero dose of the investigational drug was last administered (i.e. last week 1 date of administration + (planned interval duration of either induction or maintenance, as applicable))				
	If carboplatin or vincristine was permanently discontinued during induction, set the last date of exposure equal to the planned end date of induction.	Example 1: Subject discontinues during induction therapy. The last date of exposure is the first date of administration + 83 days.			
	If carboplatin or vincristine was permanently discontinued during maintenance, set the last date of exposure equal to the planned end date of the last cycle, last week 1 administration date + 41 days.	Example 2: Subject discontinues during maintenance therapy after receiving the week 45 dose. The week 43 (C dose 29/V dose 26) dose date was 21Jan2021. The last date of exposure is the 21Jan2021 + 41 days = 03Mar2021.			
	If carboplatin or vincristine was not permanently discontinued, set the last date of exposure equal to the data cut-off date. Note: If the patient died or was lost to follow-up before the derived last date, the last date of exposure to investigational drug is the date of death or the date of last	Example 3: if carboplatin or vincristine was not permanently discontinued prior to or on the data cut-off date, the last date of exposure is the data cut-off date			

 Table 2-7
 Definition of last date of exposure of study drug

Scenario	Definition of last date of exposure of study drug	Example
	contact, respectively. If the derived last date of exposure goes beyond the data cut-off date, it should be truncated to the date of data cut-off.	
Dabrafenib, Trametinib	Date of last administration of a non-zero dose of the study drug.	Example 4: A patient had a permanent discontinuation of the study drug on 06Jan2016 after being put on a temporary interruption since 01Jan2016. In this case the last date of exposure is 31Dec2015.

Summary of duration of exposure to each combination partner will include categorical summaries based on clinically meaningful time intervals (8-<24, 24-<56, 56-<112, >= 112 (weeks)) and using descriptive statistics (i.e. n, mean, standard deviation, median, 25^{th} - 75^{th} percentiles, minimum, and maximum) using appropriate units of time.

Cumulative dose and average daily dose

Cumulative dose of a study treatment is defined as the total dose given during the study treatment exposure and will be summarized for each of the study treatment component, respectively. Average daily dose is defined as [Cumulative dose (dosing unit) / Number of dosing days]; drug free days are not counted as dosing days.

Cumulative dose and average daily dose will be summarized both in mg and mg/kg for dabrafenib and trametinib. Total actual cumulative dose (mg/kg) of dabrafenib and trametinib is calculated as the sum of the daily doses in mg/kg, where the mg/kg dose on any particular day is calculated as the dose in mg divided by the current weight (collected as per the visit schedule). Total actual cumulative dose (mg) of dabrafenib and trametinib is calculated as the sum of the daily dose (mg) of dabrafenib and trametinib is calculated as the sum of the daily dose (mg) of dabrafenib and trametinib is calculated as the sum of the daily dose (mg) of dabrafenib and trametinib is calculated as the sum of the daily dose (mg) of dabrafenib and trametinib is calculated as the sum of the daily doses in mg.

Cumulative dose and average dose per cycle will be summarized in mg/m^2 for carboplatin and vincristine. Total actual cumulative dose of carboplatin or vincristine is calculated as the sum of the cumulative dose.

The **planned cumulative dose** for a study treatment component refers to the total planned dose as per the protocol up to the last date of study drug administration. For dabrafenib and trametinib, the planned dose (mg) will be taken from the planned dose (mg) times the frequency from the first dosing record. Planned dose for carboplatin and vincristine is defined below. The planned cumulative dose will not be summarized/listed. It will be used for relative dose intensity calculations.

The **actual cumulative dose** refers to the total actual dose administered over the duration for which the patient is on the study treatment as documented in the DAR eCRF page. For patients who did not take any drug, the actual cumulative dose is by definition equal to zero for that drug.

For continuous dosing, the actual cumulative dose is the sum of the non-zero doses recorded over the dosing period and the planned cumulative dose is the planned starting dose summed over the same dosing period.

Novartis	Confidential	Page 24
SAP Final CSR LGG		CDRB436G2201

For intermittent dosing, the actual cumulative dose should be defined based on the days when the patient is assumed to have taken a non-zero dose during dosing periods.

Dose intensity and relative dose intensity

Dose of dabrafenib and trametinib will be defined in the units of mg, and taken from the DAR eCRF. Dose of carboplatin and vincristine will be defined in units of mg/m², calculated as the administered dose received in mg/m² as taken from the DAR eCRF.

Dose intensity (DI) for patients with non-zero duration of exposure is defined as follows:

DI (*unit of dose / unit of time*) = Actual Cumulative dose (*unit of dose*) / Duration of exposure to study treatment (*unit of time*).

For dabrafenib and trametinib, the unit of dose is mg and the unit of time is days; for carboplatin and vincristine, the unit of dose is mg/m^2 and the unit of time is weeks. [Note that for subjects < 12 kg in weight, the unit of dose for vincristine is mg/kg. If such subjects are enrolled in the study, their dosing data will be summarized separately.]

For patients who did not take any drug the DI is by definition equal to zero.

Planned dose intensity (PDI) is defined as follows:

PDI (*unit of dose / unit of time*) = Planned Cumulative dose (*unit of dose*) / Duration of exposure (*unit of time*).

For carboplatin, the PDI is 116.67 mg/m²/week, based on 6-week cycles with dosing of 175 mg/m² at weeks 1 to 4 only.

For vincristine, the PDI depends on the subject's weight and also on the treatment phase.

For subjects with weight \geq 12 kg:

- during the induction phase, the PDI is 1.25 mg/m²/week, based on 1.5 mg/m² weekly *10 over 12 weeks.
- during the maintenance phase, the PDI is 0.75 mg/m²/week, based on 1.5 mg/m² weekly *3 over 6 weeks.

For subjects with weight < 12 kg:

- during the induction phase, PDI is 0.042 mg/kg/week, based on 0.05 mg/kg weekly *10 over 12 weeks.
- during the maintenance phase, the PDI 0.025 mg/kg/week, based on 0.05 mg/kg weekly *3 over 6 weeks.

Relative dose intensity (RDI) is defined as follows:

RDI (%) = [DI (unit of dose / unit of time) / PDI (unit of dose / unit of time)] x 100.

DI and RDI will be summarized separately for each of the study treatment components, using the duration of exposure of each of the components. DI and RDI will be summarized separately for induction and maintenance phase for carboplatin and vincristine.

Novartis	Confidential	Page 25
SAP Final CSR LGG		CDRB436G2201

Summary of RDI will include categorical summaries based on clinically meaningful intervals $(\leq 50\%, >50 \leq 75\%, >75 \leq 90\%, >90 \leq 110\%, >110\%)$. Note that for the purposes of DI and RDI derivation only for carboplatin and vincristine, the last date of exposure for the duration of exposure component of this calculation will not consider death date.

Table 2-8	Examples of dabrafenib dose administration and exposure					
DAR record number	Start/End Date	Dose Prescribed (mg) frequency	Dose Administered (mg) [total daily]	Dose Changes, Dose Interruption ?	Dose Permanently Discontinued	Reason
1	01Jan2016 / 05Jan2016	125 mg BID	250	No	No	
2	06Jan2016 / 03Feb2016	125 mg BID	200	Yes	No	AE
3	04Feb2016 / 25Feb2016	130 mg BID	260	Yes	No	As per protocol

Table 2-8	Examples of dabrafenib dose administration and exposure	
-----------	---	--

Duration of exposure (days) = 25Feb2016 - 01Jan2016 + 1 = 56 days

Planned cumulative dose (for 56 days) = 125*2*56 days = 14000 mg

Actual cumulative dose = 250*5 + 200*29 + 260*22 = 12770 mg

Dose intensity = 12770 mg / 56 days = 228.04 mg/day

Planned dose intensity = 14000 mg / 56 days = 250 mg/day

Relative dose intensity = DI / PDI = (228.04 mg/day) / (250 mg/day) = 91.2%

DAR record number	Start/End Date	Dose Prescribed (mg), frequency	Dose Administere d (mg) [total daily]	Dose Changes, Dose Interruption ?	Dose Permanently Discontinued	Reason
1	01Jan2016 / 10Jan2016	0.875 QD	0.875	No	No	
2	11Jan2016 / 15Jan2016	0.875 QD	0	Yes	No	AE
3	16Jan2016 / 25Feb2016	0.75 QD	0.75	Yes	No	AE

Table 2-9	Examples of trametinib dose administration and exposure
-----------	---

Duration of exposure = 25Feb2016 - 01Jan2016 + 1 = 56 days

Planned cumulative dose (for 56 days) = 0.875*56 days = 49 mg

Actual cumulative dose = 0.875*10 + 0*5 + 0.75*41 = 39.5 mg

Dose intensity = 39.5 mg / 56 days = 0.705 mg/day

Planned dose intensity = 49 mg / 56 days = 0.875 mg/day

Relative dose intensity = DI / PDI = (0.705 mg/day) / (0.875 mg/day) = 80.6%

Table 2-10	Examples of carboplatin dose administration and exposure							
Nominal Visit number	Start/End Date	Phase	Dose Prescribed (mg/m2), frequency	Dose Administered (mg) [total daily]	Dose Changes, Dose Interruption?	Dose Permanently Discontinued	Reason	
Week 1 Day 1	01Jan2016 / 01Jan2016	Induction	175 weekly	175	No	No		
Week 2 Day 1	08Jan2016 / 08Jan2016	Induction	175 weekly	0	Yes	No	AE	
Week 3 Day 1	15Jan2016 / 15Jan2016	Induction	150 weekly	150	Yes	No	AE	
